7.6.1.2 Absolute change from baseline in FVC

The absolute change from baseline in FVC – in ml, but also % pred – at week 52 will be analysed using a restricted maximum likelihood (REML) based repeated measures approach. Analyses will include the fixed, categorical effects of HRCT pattern, treatment, visit, and treatment-by-visit interaction, as well as the continuous, fixed covariates of baseline and baseline-by-visit interaction. An unstructured (co)variance structure will be used to model the within-patient measurements. In the event of non-convergence, the same methods that are used for the primary endpoint analysis as described in [Section 7.4.1](#) will be used to overcome the issue. The Kenward-Roger approximation will be used to estimate denominator degrees of freedom. The HRCT pattern will be included as a covariate (with exception when the analysis is run in the co primary population of patients with "HRCT with UIP-like fibrotic pattern only") as well as the baseline FVC value. Additionally, descriptive analyses of the absolute change from baseline will be shown, for the co-primary populations as well as for the complementary population.

7.6.1.3 Absolute decline from baseline in FVC % pred

The same type of evaluation as described in [Section 7.5.2.2.3](#) will be implemented for this endpoint.

7.6.1.4 Carbon Monoxide Diffusion Capacity (DLCO) % pred

A similar analysis based on a restricted maximum likelihood (REML) based repeated measures approach as depicted in [Section 7.6.1.2](#) will be performed for the absolute change in DLCO % pred. The HRCT pattern will be included as a covariate (with exception when the analysis is run in the co primary population of patients with “HRCT with UIP-like fibrotic pattern only”) as well as the baseline DLCO value

7.6.1.5 Living with Pulmonary Fibrosis Symptoms and Impact Questionnaire (L-PF)

The absolute change from baseline in L-PF total score between week 52 and baseline will be presented graphically as well as numerically to illustrate the impact of the underlying condition on the patient’s health status.

The absolute change from baseline in L-PF impact score between week 52 and baseline will be presented graphically as well as numerically to illustrate the impact of the underlying condition on the patient’s health status.

The absolute change from baseline in L-PF symptoms total score between week 52 and baseline will be presented graphically as well as numerically to illustrate the impact of the underlying condition on the patient’s health status.

The absolute change from baseline in L-PF symptoms fatigue domain score between week 52 and baseline will be presented graphically as well as numerically to illustrate the impact of the underlying condition on the patient’s health status.

The descriptive analyses of the absolute change from baseline in L-PF total score, L-PF impact score, L-PF symptoms total score and L-PF symptoms fatigue domain score will also be shown for the complementary population.

In addition to the descriptive evaluation, absolute change from baseline in L-PF total score between week 52 and baseline, in L-PF impact score between week 52 and baseline, in L-PF symptoms total score between week 52 and baseline and in L-PF symptoms fatigue domain score between week 52 and baseline will also be analysed using a restricted maximum likelihood (REML) based repeated measures approach. An unstructured variance-covariance structure will be used to model the within patient measurements. In the event of non-convergence, the same methods used in the primary analyses ([Section 7.4.1](#)) will be implemented to overcome the issue. The HRCT pattern will be included as a covariate (with exception when the analysis is run in the co primary population of patients with “HRCT with UIP-like fibrotic pattern only”) as well as the respective baseline L-PF score.

7.6.1.6 Pulmonary Fibrosis Impact on Quality of Life Scale (PF-IQOLS)

The absolute change from baseline in PF-IQOLS summary score (which is the average of the individual dimension ratings) between week 52 and baseline will be presented graphically as well as numerically to illustrate the impact of the underlying condition on the patient's health status. The descriptive analyses of the absolute change from baseline will also be shown for the complementary population.

In addition to the descriptive evaluation, absolute change from baseline in PF-IQOLS summary score between week 52 and baseline will also be analysed using a restricted maximum likelihood (REML) based repeated measures approach. An unstructured variance-covariance structure will be used to model the within patient measurements. In the event of non-convergence, the same methods used in the primary analyses ([Section 7.4.1](#)) will be implemented to overcome the issue. The HRCT pattern will be included as a covariate (with exception when the analysis is run in the co primary population of patients with "HRCT with UIP-like fibrotic pattern only") as well as the respective baseline PF-IQOLS summary score.

7.6.2 Over the whole trial

7.6.2.1 Time to first acute ILD exacerbation or death

The same type of evaluation as described in [Section 7.5.2.1.3](#) will be implemented, but data over the whole trial duration will be taken into consideration. Similarly, if the proportion of patients experiencing at least 1 acute ILD exacerbation is less than 5%, then only frequencies of events by treatment group will be provided for this endpoint. In this case no other analyses will be performed.

7.6.2.2 Time to death

The same type of evaluation as described in [Section 7.5.2.1.2](#) will be implemented, but data over the whole trial duration will be taken into consideration. If the proportion of patients experiencing an event is less than 5%, only frequencies of events by treatment group will be provided for this endpoint. In this case no other analyses will be performed.

7.6.2.3 Time to death due to respiratory cause

The same type of evaluation as described in [Section 7.5.2.2.1](#) will be implemented, but data over the whole trial duration will be taken into consideration. Similarly, if the proportion of such patients is less than 5%, then only frequencies of events by treatment group will be provided for this endpoint. In this case no other analyses will be performed.

7.6.2.4 Time to progression or death

The same type of evaluation as described in [Section 7.5.2.2.2](#) will be implemented, but data over the whole trial duration will be taken into consideration. Similarly, if the proportion of patients experiencing a progression is less than 5%, then only frequencies of events by treatment group will be provided. In this case no other analyses will be performed.

7.6.2.5 Time to first non-elective hospitalisation or death

The same type of evaluation as described in [Section 7.6.1.1](#) will be implemented, but data over the whole trial duration will be taken into consideration. Similarly, if the proportion of patients experiencing a non-elective hospitalisation is less than 5%, then only frequencies of events by treatment group will be provided for this endpoint. In this case no other analyses will be performed.

7.6.2.6 Descriptive evaluations of lung function parameters

Descriptive analyses of the absolute change from baseline of FVC in ml, FVC (% of predicted) and DLCO (% of predicted), as well as the relative change from baseline in FVC (% of predicted) will be shown, for the co-primary populations as well as for the complementary population.

7.6.3 Pharmacokinetics

Descriptive analysis

Trough concentrations (i.e. pre-dose concentrations) of nintedanib at Visits 4 and 7 will be used. If both concentrations are available, the geometric mean will be used. If one trough concentration value is missing or invalid, the other one will be used without adjustment. To account for potential dose reductions, all trough concentrations will be dose normalised by the actual dose taken by the patient at the time of PK sampling. The dose normalised trough concentrations for nintedanib (C_{pre,ss}_D) will be summarised descriptively. These analyses will be performed using the PKS.

7.6.4 Biomarkers

All biomarker evaluations will be specified and reported separately.

7.6.5 Longitudinal HRCT assessments

All evaluations of the optional longitudinal HRCT assessments will be specified and reported separately.

7.7 EXTENT OF EXPOSURE

Exposure will be presented based on dose received and time to first dose reduction or interruption. Reasons for dose reduction or interruption will be presented. Exposure will be summarised and presented separately over the first 52 weeks and over the whole trial. In addition, exposure will be presented for patients taking DMARDs with known hepatotoxic or gastrointestinal effects at baseline and on-treatment. Please see [Section 5.4.3](#) for details.

7.7.1 Over 52 weeks

In addition to both co-primary populations, exposure data over 52 weeks will also be summarised on the complementary patient population i.e. patients with “other HRCT fibrotic patterns”.

The duration on treatment and dose intensity will be computed overall, as well as on the individual dose strengths. A summary of treatment interruptions will be created including number of patients with at least one interruption, number and reason of interruptions, as well as time to first interruption. A similar summary will be performed for dose changes.

For the co-primary populations only, a Kaplan-Meier plot of time to premature treatment discontinuation will be produced. Similarly, Kaplan-Meier plots will be performed for time to first dose reduction and for time to first treatment interruption. No statistical tests will be performed.

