During the nintedanib trials 1199.32 and 1199.34, the most commonly reported adverse events ($\geq 10\%$ and ≥ 1.5 times placebo) experienced with nintedanib were diarrhoea (nintedanib 62.4% vs placebo 18.4%), nausea (24.5% vs 6.6%), abdominal pain (15.0% vs 6.1%), vomiting (11.6% vs 2.6%) and decreased appetite (10.7% vs 5.7%). Most of these AEs were of mild or moderate intensity, reported as non-serious, and were managed by symptomatic treatment and/or temporary interruption and/or reduction of the nintedanib

dosage. 19% of patients treated with nintedanib had an adverse event leading to treatment discontinuation (compared to 13% in the placebo treatment group). The most commonly reported adverse events ($\geq 1\%$ and more than for placebo) leading to nintedanib discontinuation were diarrhoea (4.4%), nausea (2.0%) and decreased appetite (1.4%).

Liver enzyme elevations (AST and/or ALT $\geq 3 \times$ ULN) were experienced by 5.0% of patients treated with nintedanib in the phase III trials (versus 0.7% of patients treated with placebo).

Arterial thromboembolic events were infrequently reported: in 0.7% of patients in the placebo and 2.5% in the nintedanib treated group. While adverse events reflecting ischemic heart disease were overall balanced between the nintedanib and placebo groups, within this group of terms a higher percentage of patients experienced myocardial infarctions in the nintedanib group (1.6%) compared to the placebo group (0.5%).

For further details refer to the current version of the Investigators Brochure

In conclusion: the most frequent AEs were gastrointestinal events which were manageable by the proposed dose regimen that includes dose reduction and dosing interruption. This dosing regimen was also effective in the management of liver enzyme and bilirubin elevations that are associated with nintedanib treatment.

Overall, the evidence available from the clinical development programme demonstrates a favourable benefit-risk balance for nintedanib in the treatment of patients with IPF.

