4.1.3 Selection of doses in the trial

Based on the efficacy, safety and dose-finding from trials investigating nintedanib in IPF, a dose of 150 mg bid is selected for the PF-ILD program. With 150 mg bid, acceptable tolerability in PF-ILD patients is expected based on the risk profile seen in IPF patients. Lower starting doses are not expected to demonstrate efficacy based on the dose ranging trial in IPF. However, to manage adverse events, the dose may be reduced to 100 mg bid temporarily or permanently (see [Section 4.2.1](#) and Section 6.2.4).

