4.2 CONCOMITANT THERAPY, RESTRICTIONS, AND RESCUE TREATMENT

4.2.1 Rescue medication, emergency procedures, and additional treatment(s)

Rescue medication to reverse the action of nintedanib is not available.

Dose reduction from 150 mg bid to 100 mg bid or treatment interruption should be considered to manage adverse events. No further dose reduction is possible for patients on the 100 mg bid regimen. In case of persistent adverse events observed at this dose, or severe effects at 150 mg bid, permanent treatment discontinuation should be considered.

Treatment interruption, reduction and re-increase are allowed at multiple occasions.

Table 4.2.1: 1 Allowed treatment reduction / interruption periods:

	AEs considered related to study drug	AEs not considered related to study drug
Maximum interruption	4 weeks	8 weeks
Recommended restart	with reduced dose (100 mg bid)	with the same dose as before interruption (100 mg bid or 150 mg bid)
Re-escalation	within 4 weeks to 150 mg bid	N/A

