7.3.4 Safety analyses

The primary assessment of benefit-risk of nintedanib in patients with PF-ILD will be based on efficacy and safety data over 52 weeks (using data from Part A of the trial). All safety assessments described below will focus on data collected within the first 52 weeks of the study. In addition, selected safety analyses will be repeated to include data collected beyond 52 weeks (during Part B of the trial); further details will be specified in the TSAP.

Adverse events will be coded using the Medical Dictionary for Regulatory Activities (MedDRA) coding dictionary. Standard BI summary tables and listings will be produced. All treated patients will be included in the safety analysis for the overall population and the safety analysis will be repeated for the co-primary population of patients with HRCT with UIP-like fibrotic pattern only. In general, safety analyses will be descriptive in nature and will be based on BI standards. No hypothesis testing is planned.

Kaplan-Meier plots will be produced for the time to premature treatment discontinuation, for the time to first dose reduction and for the time to first treatment interruption.

Statistical analysis and reporting of adverse events will concentrate on treatment-emergent adverse events. To this end, all adverse events occurring between start of treatment and end of the residual effect period will be considered 'treatment-emergent'. The residual effect period is defined as the 28 days after the date of the last dose of trial medication. Adverse events that start before first drug intake and deteriorate under treatment will also be considered 'treatment-emergent'. Based on the half-life of the study drug, the medical residual effect period is 7 days after the last dose of trial medication. Therefore, additional analysis of safety data will be made for adverse events that occur between the start of treatment and up to 7 days after the date of the last dose of trial medication will be analysed in addition.

Frequency, severity, and causal relationship of adverse events will be tabulated by system organ class and preferred term after coding according to the current version of MedDRA.

Summary tables will be produced for the adjudication results of MACE and deaths.

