5.4.3 Exposure

5.4.3.1 Over 52 weeks

Duration of exposure [months] = (date of last administration^[1] – date of first administration +1 day) / 30.5

[1] Or week 52 time-point (372 days after date of first trial drug intake), if earlier.

Duration of exposure in categories: ≤3 months (91 days); >3 months (91 days) to ≤ 6 months (182 days); > 6 months (182 days) to ≤12 months (365 days); > 12 months (365 days)

Treatment interruptions will not be subtracted from the duration of exposure.

Duration on actual dose (100 or 150 mg bid) (sum of durations on-treatment for each dose effectively taken): in weeks and in categories (≤ 8 weeks, > 8 weeks)

Total dose [g]: Duration of exposure [days] * actual dose [g]

Dose intensity [%]: amount of drug actually administered over the study (dose 100mg and 150mg) divided by the amount of drug that would have been administered had dose 150mg bid been administered over all the study (from date of first administration to date of last administration, whether or not trial drug was prematurely discontinued). Dose intensity will be summarized in percent and in categories (≤ 30 %, >30% - ≤50%, >50% - ≤90%, >90% - <100%, 100%).

Time to first dose reduction or time to first treatment interruption in classes : ≤ 31 days, $> 31 - \leq 91$ days, $> 91 - \leq 182$ days, > 182 days

Time to first dose reduction, time to first treatment interruption, as well as time to premature treatment discontinuation will also be evaluated via survival methods. Censoring rules can be found in Table 5.4.3.1: 1, [Table 5.4.3.1: 2](#) and [Table 5.4.3.1: 3](#) respectively.

Duration of exposure in patient years will also be shown per treatment group.

Table 5.4.3.1: 1 Censoring Rules for Time to first dose reduction over 52 weeks

Rule #	Situation	Outcome (event or censored)	Date of event or censoring
1	Patient had a documented first dose reduction within the first 52 weeks or before the treatment was prematurely ^[1] discontinued and the date of the event is known	Event	Date of event
2	Patient had a documented first dose reduction within the first 52 weeks or before the treatment was prematurely ^[1] discontinued and the date of the event is unknown	Event	Imputed date of event
3	Patient did not have a documented first dose reduction within the first 52 weeks or before the treatment was prematurely ^[1] discontinued	Censored	Earliest of Day 373 (372 days after first drug intake) or date of permanent premature ^[1] drug discontinuation

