5.4.3.2 Over the whole trial

Similarly, duration of exposure, duration on actual dose, total dose and dose intensity will be summarized over the whole trial. Time to first dose reduction and time to first interruption will also be computed and shown.

Over this period, the categories for the duration of exposure will be: ≤ 3 months (91 days); > 3 months (91 days) to ≤ 6 months (182 days); > 6 months (182 days) to ≤ 12 months (365 days); > 12 months (365 days) to ≤ 18 months (547 days); > 18 months (547 days) to ≤ 24 months (730 days); > 24 months (730 days)

Time to first dose reduction, time to first treatment interruption, as well as time to premature treatment discontinuation will also be evaluated via survival methods. Censoring rules can be found in [Table 5.4.3.2: 1](#), [Table 5.4.3.2: 2](#) and [Table 5.4.3.2: 3](#) respectively.

Duration of exposure in patient years will also be shown per treatment group.

Table 5.4.3.2: 1 Censoring Rules for Time to first dose reduction over the whole trial

Rule #	Situation	Outcome (event or censored)	Date of event or censoring
1	Patient had a documented first dose reduction before the treatment was permanently discontinued or the patient switched into the extension trial and the date of the event is known	Event	Date of event
2	Patient had a documented first dose reduction before the treatment was permanently discontinued or the patient switched into the extension trial and the date of the event is unknown	Event	Imputed date of event
3	Patient did not have a documented first dose reduction before the treatment was permanently discontinued or the patient switched into the extension trial	Censored	Earliest date of permanent drug discontinuation, database lock or date of Informed Consent in extension trial ^[1]

^[1] Date of Informed Consent in extension trial is not applicable for the primary analysis.

Table 5.4.3.2: 2 Censoring Rules for Time to first treatment interruption over the whole trial

Rule #	Situation	Outcome (event or censored)	Date of event or censoring
1	Patient had a documented first treatment interruption before the treatment was permanently discontinued or the patient switched into the extension trial and the date of the event is known	Event	Date of event
2	Patient had a documented first treatment interruption before the treatment was permanently discontinued or the patient switched into the extension trial and the date of the event is unknown	Event	Imputed date of event

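### Kaplan-Meier curves for first dose reduction and first interruption censor at permanent discontinuation, so they overstate these probabilities in each arm; the effect is small and confined to descriptive exposure displays

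*SAP*

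**What the plan says.** SAP section 7.7.1, after a Kaplan-Meier plot of time to premature discontinuation, adds: "Similarly, Kaplan-Meier plots will be performed for time to first dose reduction and for time to first treatment interruption". This follows protocol section 7.3.4: "Kaplan-Meier plots will be produced for the time to premature treatment discontinuation, for the time to first dose reduction", with first interruption named next.

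The censoring rules are in SAP section 5.4.3. Over 52 weeks, rule 3 of Tables 5.4.3.1: 1 and 5.4.3.1: 2 censors a patient without the event at "Earliest of Day 373 (372 days after first drug intake) or date of permanent premature" drug discontinuation. Over the whole trial, rule 3 of Tables 5.4.3.2: 1 and 5.4.3.2: 2 uses "Earliest date of permanent drug discontinuation, database lock or date of Informed Consent in extension trial". Section 5.4.3.2 calls for survival methods for these endpoints. Section 7.7.2 summarises whole-trial exposure in the same way as the 52-week period, without naming the plot again.

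Section 7.7.1 also tabulates how many patients had at least one interruption, with a similar summary for dose changes, and rules out statistical tests. Neither document mentions competing risks for these endpoints.

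**The concern.** Discontinuation is not ordinary loss to follow-up here: it ends the possibility of the event. It can also come before any reduction or interruption. Protocol section 4.2.1 states: "In case of persistent adverse events observed at this dose, or severe effects at 150 mg bid, permanent treatment discontinuation should be considered". Signs of hepatic injury likewise lead straight to withdrawal (protocol section 4.2.1.2).

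Censoring at that point and plotting one minus Kaplan-Meier treats those who stopped as if they could still be reduced or interrupted later, at the same rate as those still on drug. The result is not the share of treated patients who had the event. It is also hard to defend as the risk had treatment continued, because that needs non-informative censoring, while adverse events drive reduction, interruption and discontinuation alike.

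Dose reduction and interruption are the protocol's tools for managing adverse events, so these curves are part of the tolerability picture. A reader will probably take percentages off them and compare the arms.

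**Working it through.** The plan states no probability for these curves, so there is no figure to reproduce.

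**Mechanism.** Suppose that of 100 patients 19 stop first, and 30 of the remaining 81 later have a reduction. The actual proportion is 30/100 = 30%. One minus Kaplan-Meier is 30/81 = 37.0%. This ordering is extreme, but the sign is general: one minus Kaplan-Meier cannot fall below the cumulative incidence, and it exceeds it whenever events occur after a discontinuation by an event-free patient. No independence assumption is needed. Over 52 weeks the rules censor only at Day 373 or at discontinuation, so the crude percentage of treated patients is itself the cumulative incidence.

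**Inputs.**
- Discontinuation: protocol section 1.2 gives, for the IPF phase III trials, 19% on nintedanib and 13% on placebo, for adverse events only. As constant hazards m per year: −ln(1 − 0.19) = 0.211 and −ln(1 − 0.13) = 0.139.
- Relevance of IPF: protocol section 4.1.3 relies on it ("acceptable tolerability in PF-ILD patients is expected based on the risk profile seen in IPF patients").
- Risk of first reduction or interruption: not given. Assumed 10–40% on nintedanib and 2–10% on placebo, plus a null case of 15% in both arms.

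**Formulas**, with l the hazard of the event:
- one minus Kaplan-Meier = 1 − exp(−l)
- cumulative incidence = l/(l + m) × [1 − exp(−(l + m))]

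**Example.** For a true 30% on nintedanib, l = 0.401. Cumulative incidence = 0.401/0.612 × [1 − exp(−0.612)] = 30.0%, and one minus Kaplan-Meier = 1 − exp(−0.401) = 33.0%. For a true 4% on placebo, l = 0.0438, and one minus Kaplan-Meier is 4.3%.

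**Results**, nintedanib/placebo. The last column halves both discontinuation hazards, to represent half of the discontinuations coming before the event.

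| Assumed true risk | 1 − KM | True difference | KM difference | Excess (points) | Excess, hazards halved |
|---|---|---|---|---|---|
| 10% / 2% | 11.1% / 2.1% | 8.0 | 8.9 | 0.9 | 0.5 |
| 20% / 5% | 22.1% / 5.4% | 15.0 | 16.7 | 1.7 | 0.9 |
| 30% / 4% | 33.0% / 4.3% | 26.0 | 28.8 | 2.8 | 1.4 |
| 30% / 10% | 33.0% / 10.7% | 20.0 | 22.3 | 2.3 | 1.2 |
| 40% / 10% | 43.9% / 10.7% | 30.0 | 33.2 | 3.2 | 1.6 |
| 40% / 5% | 43.9% / 5.4% | 35.0 | 38.6 | 3.6 | 1.8 |
| 15% / 15% | 16.6% / 16.0% | 0.0 | 0.5 | 0.5 | 0.3 |

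**Variations.**
- Equal discontinuation of 13% in both arms: the excess is still 0.6 (10%/2%), 1.7 (30%/4%) and 1.3 (30%/10%) points, because the bias also grows with the event hazard.
- Front-loaded hazards (simulated, Weibull shape 0.6), 30%/4% case: again about 33.0% and 4.3%.
- Nintedanib discontinuation hazard cut to a half or a quarter, placebo left in full: the excess falls to between 0.05 and 1.2 points for risks of 10%/2% to 40%/10%. It turns negative only when the risks are close: −0.3 for 15%/10% (quarter), and −0.3 and −0.6 for 15%/15% (half and quarter).

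**The case against.** The strongest reply is that the correct 52-week figure is already planned. Section 7.7.1 tabulates patients with interruptions and dose changes, section 5.4.3.1 adds time to first event in classes, and the competing event has its own Kaplan-Meier curve. A curve censored at drug stop can also be read as showing the on-drug rate, and the SAP never says that it estimates the proportion of all treated patients. This stands in part: for 52 weeks a clear label would remove much of the problem. It does not fully answer the point. Counts in classes are a coarse time course, and in the whole-trial period, where follow-up varies, crude percentages are not risks at a fixed time.

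A second reply is that many discontinuations come after the event. The protocol's pathways for persistent adverse events at the reduced dose (4.2.1), for severe diarrhoea (4.2.1.1) and for moderate liver enzyme elevation (4.2.1.2) generally put reduction or interruption first. Those patients have had at least one of the two events and are not censored for it. This stands, and it makes the full-hazard results an upper end.

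A third reply is sampling error. With 300 per arm and risks of 30% and 4%, the standard error of the difference is √(0.30 × 0.70/300 + 0.04 × 0.96/300), about 2.9 points, so the bias is at most about one standard error. This also stands.

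A reader might infer that discontinuation is known to be more frequent on nintedanib in this trial, and that the curves must therefore exaggerate the difference between arms. The documents support neither. The 19% and 13% are adverse-event discontinuations in IPF. All-cause discontinuation in PF-ILD, and the share that precedes a first reduction or interruption, are not given.

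**Conclusion.** The point holds for each arm: with these censoring rules the Kaplan-Meier curves overstate the probability of a first reduction or interruption whenever such events follow a discontinuation by an event-free patient, and the 52-week curve will then differ from the crude percentage beside it. That part needs no assumed rates.

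The size and the effect on the difference between arms do rest on assumptions. With the IPF discontinuation rates and the assumed event risks, an excess of about 0.5 to 3 points is probable. The most extreme cell reaches 3.6, and the excess is less if most discontinuations follow a reduction or interruption. Overstatement of the difference is likely, since diarrhoea in IPF (62.4% against 18.4%, protocol section 1.2) suggests a higher event rate on nintedanib. It is not certain: the sign can reverse when the arms' risks are close and far fewer nintedanib discontinuations come first.

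The consequence is limited to descriptive exposure displays. The crude counts are unaffected, and no test, efficacy result or dosing rule changes. This is a cheap improvement, not a flaw in the trial's conclusions.

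**What to change.** For both analysis periods, replace the Kaplan-Meier plots of first dose reduction and first interruption with Aalen-Johansen cumulative incidence curves:
- Treat permanent discontinuation, including death, as the competing event, and amend rule 3 of Tables 5.4.3.1: 1–2 and 5.4.3.2: 1–2 accordingly.
- Keep Day 373, database lock and rollover to the extension trial as censoring.
- Keep Kaplan-Meier for time to premature discontinuation.
- State in section 7.7.2 that the same curves are produced over the whole trial.
- List the change under SAP section 4.2, since protocol section 7.3.4 names Kaplan-Meier.

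If the Kaplan-Meier curves are kept because the protocol names them, label them as on-drug curves censored at discontinuation and show the cumulative incidence beside them.

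The cost is SAP wording and a standard procedure option, with no new data. The one drawback is a documented departure from the plot type in the protocol, which the second option avoids.
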